3 STUDY DESIGN AND PLAN

[figure not shown]
3.1 Overall Study Design and Plan

3.1.1 General Study Design

This study is a Phase 1, open-label, dose escalation, and cohort expansion study designed to characterize the safety, tolerability, PK, PD, immunogenicity, and preliminary antitumor activity of MGA271 administered IV weekly in combination with pembrolizumab administered IV Q3W. Beginning with Amendment 5, this study also characterizes the safety and tolerability of MGA271 administered IV Q3W in combination with MGA012, both administered IV Q3W (cohort 4).

This study consists of a Dose Escalation Phase to determine the MTD or MAD (if no MTD is determined) of MGA271 administered in combination with 2 mg/kg pembrolizumab, followed by a Cohort Expansion Phase to further define the safety and initial efficacy of the combination with the MGA271 dose established in the first phase. The study treatment schema is presented in **Figure 1**.

Figure 1 MGA271 + Pembrolizumab Treatment Schema

a Patients may receive up to 5 subsequent 9-week treatment cycles of MGA271 + pembrolizumab depending on response to study treatments

* All patients will enter an Efficacy Follow-up Period after receipt of the last dose of study treatment to be followed for up to 24 weeks for survival.

[figure not shown]
MGA271 will be administered as an IV infusion over 120 minutes on a once-weekly schedule. Pembrolizumab will be administered at 2 mg/kg as an IV infusion over 30 minutes Q3W. On the days that both agents are administered, pembrolizumab will be administered first, followed by MGA271.

For both the Dose Escalation and Cohort Expansion phases, the first tumor assessment will be obtained on Cycle 1 Study Day 42 of the Initial Tumor Assessment Cycle.

Patients who remain clinically stable and do not experience unacceptable toxicity that necessitates permanent discontinuation of the study drugs, at the completion of the Initial (6-week) Tumor Assessment Cycle will be eligible to receive additional treatment with pembrolizumab and MGA271. Assuming that the patient remains clinically stable, maintains a response status of SD or better, and does not experience unacceptable toxicity that necessitates permanent discontinuation of the study drugs, patients may receive up to 5 additional 9-week treatment cycles during Subsequent Tumor Assessment Cycles, for a maximum total of 51 doses of MGA271 and 17 doses of pembrolizumab.

Beginning with Amendment 5, in Cohort 4, 15 mg/kg MGA271 will be administered as an IV infusion over 120 minutes Q3W in combination with 375 mg MGA012 administered as an IV infusion over 60 to 75 minutes Q3W. On dosing days, MGA012 will be administered first, followed by MGA271. The study treatment schema is presented in **Figure 2**.

Figure 2 MGA271 + MGA012 Treatment Schema: Cohort 4

a Patients may receive up to 5 subsequent 9-week treatment cycles of MGA271 + MGA012 depending on response to study treatments

▲ All patients will enter an Efficacy Follow-up Period after receipt of the last dose of study treatment to be followed for up to 24 weeks for survival.

Patients who remain clinically stable and do not experience unacceptable toxicity that necessitates permanent discontinuation of the study drugs, at the completion of the Initial (6-week) Tumor Assessment Cycle, will be eligible to receive additional treatment with MGA271+MGA012. Assuming that the patient remains clinically stable, maintains a response status of SD or better, and does not experience unacceptable toxicity that necessitates permanent discontinuation of the study drugs, patients may receive up to 5 additional 9-week treatment cycles during Subsequent Tumor Assessment Cycles, for a maximum total of 17 doses of MGA271 and 17 doses of MGA012.

All tumor assessments performed following the Initial Tumor Assessment Cycle will occur on Study Day 63 of each Subsequent Tumor Assessment Cycle thereafter. Following the last dose of study drug, all patients will be followed for survival during a 6-month (24-week)

Efficacy Follow-up Period. Patients who discontinue study treatment for a reason other than progressive disease may be followed for efficacy and survival beyond the 6-month (24-week) period until 1 of the following occurs: the patient progresses, withdraws consent for follow up, or initiates other anti-cancer therapy, or the overall trial is closed.

3.1.2 Dose Escalation Phase

The goal of the Dose Escalation Phase is to initially characterize the safety and tolerability of MGA271 and pembrolizumab administered in combination, and more specifically to describe the DLTs for each dose level studied and to define the MTD or MAD (if no MTD is defined) based on the frequency of occurrence of DLTs in each cohort. Patients with mesothelioma, urothelial cancer, NSCLC, SCCHN, melanoma, thyroid cancer, TNBC, colon cancer, soft tissue sarcoma, or prostate cancer will be enrolled in the Dose Escalation Phase.

For the purposes of guiding decisions regarding dose escalation, the DLT Evaluation Period is defined as the time following administration of the first dose of pembrolizumab to the day of the third planned administration of pembrolizumab (i.e., Cycle 1/Initial Tumor Assessment Cycle).

The dose escalation will follow a conventional 3+3+3 design: MGA271 will be evaluated in sequential escalating doses ranging from 3 mg/kg to 15 mg/kg in combination with 2 mg/kg pembrolizumab in cohorts of 3 to 9 patients each. Dose levels of MGA271 to be evaluated include 3 mg/kg (starting dose), 10 mg/kg, and 15 mg/kg. If it is determined that the MTD is exceeded in the first dose cohort, a dose de-escalation cohort to evaluate a lower dose of MGA271 (1 mg/kg) in combination with 2 mg/kg pembrolizumab will be enrolled. The drug doses in each cohort are listed in **Table 1**.

Table 1 MGA271 Dose Escalation Cohorts

Cohort	MGA271 Dose	Pembrolizumab Dose	MGA012
Cohort 1 ^a	1 mg/kg	2 mg/kg	N/A
Cohort 1	3 mg/kg (starting dose)	2 mg/kg	N/A
Cohort 2	10 mg/kg	2 mg/kg	N/A
Cohort 3	15 mg/kg	2 mg/kg	N/A
Cohort 4	15 mg/kg	N/A	375 mg

a To be evaluated only if the starting dose is determined to exceed the MTD.

An intermediate dose of MGA271 may be explored selectively during the dose escalation portion of the study, based on review of the cumulative safety, efficacy, and/or PK data on the respective arms and based upon agreement between the investigators and the Sponsor as follows:

- If Cohort 2 exceeds the MTD the following dose level may be evaluated:
 - Cohort 1a: 7 mg/kg MGA271 + 2 mg/kg pembrolizumab (n=3-9 patients)

- If Cohort 3 exceeds the MTD the following dose levels may be evaluated:
 - Cohort 2a: 12 mg/kg MGA271 + 2 mg/kg pembrolizumab (n=3-9 patients)

Any escalation cohort, not exceeding the MTD, can be expanded to a maximum of 15 patients for further evaluation of safety and efficacy.

The MTD for MGA271 will be defined as the dose level at which < 33% of patients experience a drug-related DLT during the DLT evaluation period. If no MTD is defined for the combination of MGA271 and pembrolizumab after escalation to the maximum protocol-specified dose, that dose level will be designated as the MAD.

Beginning with Amendment 5, a new cohort, Cohort 4, was added to explore safety and tolerability of MGA271+MGA012 administered in combination. Since MTD was not reached for the MGA271+pembrolizumab cohorts, 15 mg/kg was determined as the maximum administered dose (MAD) for MGA271. Patients will receive 15 mg/kg MGA271 (MAD) in combination with a flat-dose of 375 mg MGA012, with both study drugs administered on a Q3W schedule ([Table 1](#)).

For the purposes of guiding decisions regarding dose escalation, the DLT Evaluation Period is defined as the time following administration of the first dose of MGA271 plus MGA012 to the day of the third planned administration of MGA012 (i.e., Cycle 1 /Initial Tumor Assessment Cycle).

Enrollment in Cohort 4 will follow a conventional 3+3+3 design. If the 15 mg/kg MGA271 + 375 mg MGA012 combination dose is deemed tolerable, additional patients may be added for up to a total of 15 dose evaluable patients in the cohort. No higher doses of the combination are planned. If the 15 mg/kg MGA271 +375 mg MGA012 combination dose level is found to exceed the MTD, de-escalation to 10 mg/kg MGA271+375 mg MGA012 may be explored and if that dose level were to exceed the MTD, a further de-escalation to 3 mg/kg MGA271+375 mg MGA012 may be explored following the same conventional 3+3+3 design. Any of these dose levels, not exceeding the MTD, can be expanded up to a maximum of 15 patients for further evaluation of safety and efficacy.

3.1.3 Cohort Expansion Phase

During the Cohort Expansion Phase, additional cohorts of patients with unresectable, locally-advanced or metastatic melanoma (up to n=16), 2 cohorts of NSCLC (up to n=20 each), 2 cohorts of SCCHN (up to n=20 each), or urothelial cancer (up to n=16) will be enrolled to receive MGA271 in combination with pembrolizumab at the MTD (or MAD) established from the Dose Escalation Phase of the study. The goals for this portion of the study will be to:

1. Further characterize the safety MGA271 in combination with pembrolizumab at the MTD (or MAD);

2. Further evaluate the PK, PD, and immunogenicity of MGA271 in combination with pembrolizumab; and
3. Provide a preliminary assessment of the antitumor activity of MGA271 in combination with pembrolizumab in patients with advanced melanoma, NSCLC, SCCHN, or urothelial cancer.

3.1.4 Efficacy Follow-up Period

The Efficacy Follow-up Period consists of the 6-month (24-week) period following the final dose of study drug (pembrolizumab or MGA271 or MGA012, whichever is last) where patients will be followed for survival via telephone or other electronic contact at 12-week intervals from the start of the period. Patients who discontinue study treatment for a reason other than progressive disease may be followed for efficacy and survival until 1 of the following occurs: the patient progresses, withdraws consent for follow up, or initiates other anti-cancer therapy, or the overall trial is closed.

3.2 Sample Size Justification

This study may enroll up to 157 patients (up to approximately 45 in the dose escalation phase and 112 in the MTD expansion cohorts). This sample size is considered sufficient to evaluate the primary objective of this study (toxicity). In addition,

mors.

Additional patients may be enrolled in study groups to meet sample size requirements if discontinuations unrelated to treatment-emergent signs and symptoms occur.

For the Cohort Expansion Phase, up to 16 patients each will be enrolled into melanoma and urothelial expansion cohorts, respectively, and up to 20 patients will be enrolled into each of 2 cohorts for NSCLC and SCCHN, respectively.

4 STUDY POPULATIONS AND SUBGROUPS

4.1 Study populations

Two populations will be used for analysis, the Safety Population and the Response Evaluable Population, as defined below:

- **Safety Population:** All patients who received at least one dose of MGA271, pembrolizumab or MGA012. Safety Population will be used to summarize baseline data, safety data and for assessment of overall survival (OS) and progression-free survival (PFS). Patients who receive at least one dose of MGA271 or MGA012 will be included in PK, PD, and immunogenicity analyses.
- **Response Evaluable Population:** All patients who received MGA271 and pembrolizumab, or MGA271 and MGA012, and had at least 1 post-infusion radiographic tumor assessments. Patients who meet these criteria will be eligible for the determination of best overall response and will be included in the response evaluable population used for the calculation of objective response rates (ORRs) using both conventional RECIST 1.1 and irRC criteria.

Patients who withdraw before receiving all protocol-specified treatment before completion of the DLT evaluation period, for a reason unrelated to drug toxicity will be considered to have inadequate data to support dose escalation. In this case, replacement patients may be enrolled at the same dose level and schedule as necessary to complete the cohort.

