4.7.1 Patient Accrual

The number of patients enrolled in the Dose Escalation Phase cannot be precisely determined in advance, and could range from 9 to 45 or more patients depending on results in the course of the trial and the number of MG271 doses explored. This patient number does not take into account patient replacement for non-evaluable patients or the possibility of expanding an individual escalation cohort to 15 patients to allow for further evaluation of safety, PK and antitumor activity of the combination of MGA271 and pembrolizumab at the dose level in that cohort.

The Cohort Expansion Phase of the trial will enroll 112 patients, with a target of 16 to 20 patients into each of 6 cohorts: two cohorts of patients with NSCLC (up to 20 patients in each cohort), two cohorts of patients with SCCHN (up to 20 patients in each cohort), one

cohort of patients with melanoma (up to 16 patients), and one cohort of patients with urothelial cancer (up to 16 patients). This number of patients does not take into account patients who may be replaced. During the Expansion Portion of the study, patients who withdraw before completing the first tumor assessment for a reason other than progression of disease may be considered unevaluable for response. In these cases, replacement patients may be enrolled in the same dose level as required to complete the cohort.

For planning, the maximum number of patients to be enrolled on this trial is anticipated to be approximately 157 patients.

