7.11.1.2 Objective Response and Response Duration

Target and non-target lesions will be designated and evaluated using both conventional RECIST 1.1 criteria ([Appendix 5](#)) and immune-related response criteria ([Appendix 6](#)) as noted above for the purposes of statistical analysis. Objective responses will be categorized as CR, PR, SD, or PD for conventional RECIST 1.1 criteria and irCR, irPR, irSD, and irPD for the immune-related response criteria. Determination of the objective response rate will be calculated based on the proportion of response evaluable patients achieving CR or PR using the respective criteria, when such responses are confirmed by a subsequent scan obtained at least 28 days after the initial documentation of objective response. Response-evaluable patients will include those patients who have measurable disease and have had a baseline tumor assessment and at least 1 on-treatment tumor assessments (see [Appendix 1](#)). Objective responses that are not subsequently documented with a confirmatory CT or MRI scan (e.g., unconfirmed responses) will not be included as an objective response for the purpose of calculating overall objective response rates. Response duration will be calculated from the time of initial response (CR or PR) documentation (in patients who have a subsequent confirmation of objective response) to the time of progressive disease or death, whichever occurs first.

A patient's response duration will be censored if at the time of last antitumor assessment response is ongoing. Patients who discontinue study treatment for a reason other than progressive disease may be followed for efficacy until 1 of the following occurs: the patient progresses, withdraws consent for follow up, or initiates other anti-cancer therapy, or the overall trial is closed.

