8.3 End of Treatment Visit

A list of evaluations to be performed for the End of Treatment visit is provided in [Appendix 1](#). Criteria for triggering the End of Treatment visit are specified in [Section 5.3](#). The End of Treatment Visit should be performed after the patient has met off-study criteria or has been followed for at least 28 days after the last dose of study drug depending on ability to follow the patient and duration and severity of ongoing AEs. It is recognized that certain patients (such as those experiencing progression of disease) may be cared for in facilities other than the participating investigational site, may proceed to receive other cancer therapy, and/or may elect not to return to the investigational site. Therefore, this visit is considered optional, but should be carried out whenever possible.

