Appendix 3 Definition of PFS

Situation	Date	Outcome
No baseline tumor assessments	Date of 1 st dose	Censored
Death prior to the 1 st scheduled tumor assessment	Date of death	Progressed
No post-baseline tumor assessments in absence of death prior to the 1 st scheduled tumor assessment	Date of 1 st dose	Censored
Documented disease progression	Date of disease progression	Progressed
Initiation of alternative anti-cancer treatments in absence of PD	Date of last tumor assessment prior to initiation of such treatment	Censored
Death or progression immediately after missing two or more consecutive scheduled tumor assessments	Date of last tumor assessment prior to missed assessments	Censored

**Appendix 4 Eastern Cooperative Oncology Group (ECOG)
Performance Status**

Grade	Description
0	Fully active, able to carry on all pre-disease performance without restriction.
1	Restricted in physically strenuous activity, but ambulatory and able to carry out work of a light or sedentary nature (e.g., light house work or office work)
2	Ambulatory and capable of all self-care, but unable to carry out any work activities. Up and about more than 50% of waking hours.
3	Capable of only limited self-care, confined to bed or chair more than 50% of waking hours.
4	Completely disabled. Cannot carry-on any self-care. Totally confined to bed or chair.
5	Dead

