5 ENDPOINTS AND COVARIATES

5.1 Efficacy Endpoints

Response will be categorized as complete response (CR), partial response (PR), stable disease (SD), or progressive disease (PD) and evaluated using RECIST 1.1 criteria and as immune-related complete response (irCR), immune-related partial response (irPR), immune-related stable disease (irSD), or immune-related progressive disease (irPD) using irRC. The ORR will be the proportion of patients in the response evaluable population achieving CR or PR when such responses are confirmed at least 28 days after the initial observation of an objective response. A two-sided 95% exact binomial confidence interval will be calculated around the ORR for each expansion cohort.

Duration of response (DoR) will be calculated for responders as the time from initial response (CR or PR) to the time of PD or death, whichever occurs first. Kaplan-Meier methods will be used to estimate DoR over time and the median DoR. Responders who complete the study without documented PD will be censored at the date of their last tumor assessment.

PFS and irPFS will be calculated as the time from the initial infusion of pembrolizumab or MGA271 until documented disease progression, or death from any cause. Patients with no PFS event (disease progression or death from any cause) will be censored at the date of their last tumor assessment. In addition, PFS and irPFS rates will be calculated at 3-month and 6-month year time points from the first dose of study drug. Kaplan-Meier methods will be used to estimate PFS over time and the median duration of PFS. The method of Brookmeyer and Crowley (1) will be used to construct 95% CIs around PFS estimates of the median and other quartiles for each expansion cohort.

Incomplete and missing data can complicate interpretation of PFS. **Table 3** describes the handling of these data for the PFS analysis.

Overall survival (OS) is defined as the time from the initial infusion of pembrolizumab or MGA271 to death from any cause. Kaplan-Meier methods will be used to estimate the overall survival function. Patients who do not die will be censored at the date that the patient was last known to be alive. In addition, OS will be calculated at 6 months from the first dose of study drug.

Table 3 Censoring Rules for PFS Analysis

Situation	Date	Outcome
No baseline tumor assessments	Date of 1 st dose	Censored
Death prior to the 1 st scheduled tumor assessment	Date of death	Progressed

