No post-baseline tumor assessments in absence of death	Date of 1 st dose	Censored

Situation	Date	Outcome
prior to the 1 st scheduled tumor assessment		
Documented disease progression	Date of disease progression	Progressed
Initiation of alternative anti-cancer treatments in absence of disease progression	Date of last tumor assessment prior to initiation of such treatment	Censored
Death or disease progression immediately after missing two or more consecutive scheduled tumor assessments	Date of last tumor assessment prior to missed assessments	Censored

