6.6 Efficacy Endpoint Analyses

6.6.1 Objective Response

Objective response rate (ORR), determined by RECIST and irRC criteria, will be calculated by [REDACTED] tumor type and will be based on a confirmed response at least 28 days after initial observation of response. Two-sided 95% exact binomial confidence intervals (CIs) will be calculated around the ORRs. [REDACTED]
[REDACTED]
[REDACTED]

[REDACTED] For SCCHN and NSCLC, ORR from participants with or without prior PD-1/PD-L1 treatments will be summarized in separate tumor type groups. [REDACTED]
[REDACTED]
[REDACTED]

Objective responses that are not subsequently documented with a confirmed response by CT or MRI scan (e.g. unconfirmed responses) will not be included as an objective response for the purpose of calculating overall objective response rates. Response rate will be calculated as:

Objective response rate (ORR) = number of patients with confirmed response (CR or PR) / number of patients with response evaluable

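### The ORR denominator leaves out treated patients with no scan after dosing, and row 3 of the PFS censoring table, read literally, erases deaths of unscanned patients after Day 42

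*SAP*

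**What the plan says.** **ORR.** SAP 4.1 and Protocol 9.2.1 put a patient in the Response Evaluable Population if the patient received both drugs of the combination and "had at least 1 post-infusion radiographic tumor assessments". SAP 6.6.1 defines ORR as "number of patients with confirmed response (CR or PR) / number of patients with response evaluable", and SAP 5.1 uses the same denominator. Protocol 7.11.1.2 describes evaluability differently: measurable disease, with "a baseline tumor assessment and at least 1 on-treatment tumor assessments". The first scan is scheduled for Study Day 42. A scan is also listed at the End of Treatment visit, but Protocol 8.3 says that "this visit is considered optional, but should be carried out whenever possible". For the expansion cohorts, Protocol 4.7.1 says that "patients who withdraw before completing the first tumor assessment for a reason other than progression of disease may be considered unevaluable for response", and allows replacement.

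**PFS.** PFS is analysed in all treated patients. SAP 5.1 runs it "until documented disease progression, or death from any cause". The censoring rules are in SAP Table 3, which matches Protocol Appendix 3:

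- Row 2: a death before the first scheduled assessment is an event on the date of death.
- Row 3 opens "No post-baseline tumor assessments in absence of death" and goes on to limit that absence to deaths before the first scheduled assessment (in Appendix 3, "No post-baseline tumor assessments in absence of death prior to the" first scheduled assessment). The outcome is censoring at first dose.
- Last row: a death or progression straight after two or more consecutive missed assessments is censored at the last assessment before them.

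**The concern.** A patient who fails before any scan cannot be a confirmed responder. Removing such patients therefore shrinks the ORR denominator and never the numerator. Protocol 4.7.1 points the other way: it offers unevaluable status to early withdrawals for reasons other than progression, which implies that early progressors stay in. An End of Treatment scan would bring some of them back, but the visit is optional, and Protocol 8.3 itself names patients with progression among those who may not return. Whether such a scan counts is also unclear, because one definition asks for a post-infusion scan and the other for an on-treatment scan.

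For PFS, an unscanned patient who dies on Day 60, say, fails row 2 because the death is too late, and meets row 3 because there was no death before Day 42. The death disappears, against the definition in SAP 5.1.

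The cohorts have at most 16 or 20 patients, so one or two patients are visible in the estimates. Protocol Table 1 already compares the study's ORRs favourably with anti-PD-1 monotherapy, and a denominator that can err in only one direction weakens that use.

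**Working it through.** **The plan's own figures.** Protocol Table 1 gives ORR 33.3% with N = 18 (SCCHN) and 35.7% with N = 14 (NSCLC). The only whole-number counts that fit are 6/18 and 5/14. The protocol does not say how many patients were treated in those groups or whether these Ns are evaluable counts, so the bias in Table 1, if any, cannot be computed.

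**ORR.** With x responders among n treated and k unscanned, the evaluable rate is x/(n − k). The all-treated rate x/n is thus multiplied by n/(n − k). Cohort caps (20 and 16) come from SAP 3.1.3. The responder counts and k are assumptions. Intervals are two-sided 95% exact (Clopper-Pearson), the SAP's method.

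| k | n = 20, x = 5 | n = 16, x = 4 |
|---|---|---|
| 0 | 25.0% (8.7–49.1) | 25.0% (7.3–52.4) |
| 1 | 5/19 = 26.3% (9.1–51.2) | 4/15 = 26.7% (7.8–55.1) |
| 2 | 5/18 = 27.8% (9.7–53.5) | 4/14 = 28.6% (8.4–58.1) |
| 3 | 5/17 = 29.4% (10.3–56.0) | 4/13 = 30.8% (9.1–61.4) |

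The factor runs from 20/19 = 1.05 to 16/13 = 1.23, a shift of about 1 to 6 points.

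**Where row 3 acts alone.** Cycle 2 Day 1 is Study Day 43 (Protocol Table 5). The second scan is on Day 63 of that cycle, so it falls on Study Day 43 + 62 = 105. An unscanned patient who dies on Days 43 to 105 has missed one scan, so the two-or-more-missed row does not apply. By the SAP 6.6.3 formula, a death on Study Day 60 is an event at 60/(365.25/12) = 1.97 months. Under row 3 it becomes a censored time of 1/(365.25/12) = 0.03 months.

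**PFS example (all counts assumed).** Take n = 20: one death on Day 30 (an event under row 2), 5 progressions on Day 42, m unscanned deaths on Day 70, 4 progressions on Day 105, 2 on Day 168, and the rest progression-free past 6 months. There is no other early censoring. Three months is Day 91 and six months Day 183. Each cell shows death as an event → row 3 taken literally.

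| | m = 1 | m = 2 |
|---|---|---|
| Day 60 | 14/20 = 70.0% → 13/19 = 68.4% | 14/20 = 70.0% → 12/18 = 66.7% |
| 3 months | 13/20 = 65.0% → 13/19 = 68.4% | 12/20 = 60.0% → 12/18 = 66.7% |
| 6 months | 7/20 = 35.0% → 7/19 = 36.8% | 6/20 = 30.0% → 6/18 = 33.3% |

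The median is Day 105 in every case. Row 3 takes the patient out of the risk set from the start. The curve is therefore slightly low before the death and too high after it, by the factor n/(n − m). A death after about Day 91 affects the 6-month rate but not the 3-month rate.

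The simple factor needs the absence of other early censoring. With m = 1 and two other patients censored on Day 50, 3-month PFS goes from 14/20 × 11/12 = 64.2% to 13/19 = 68.4%. Six-month PFS goes from 14/20 × 5/12 = 29.2% to 13/19 × 5/11 = 31.1%.

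**The case against.** The strongest reply is that the response-evaluable set is defined in advance and used consistently in both documents, for a secondary, descriptive endpoint in a Phase 1 trial. That is true, and it is why the evaluable ORR should stay. It does not make the omission of early failures neutral.

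- Protocol 4.7.1 is a permissive accrual rule and does not state that early progressors remain evaluable. That is an inference, though a natural one.
- An all-treated ORR also counts as non-responders patients who withdrew for unrelated reasons and were replaced, which can pull the rate down. This is a fair point; showing both figures lets the reader see the range.
- Parts of SAP 6.6.1 are blacked out, and an all-treated ORR could be there. This cannot be excluded. It would not affect row 3 or the wording mismatch.
- Row 3 may be meant as no scan and no death at all. Probably so, but programmers work from the text, and the text says otherwise.
- The Day 43 to 105 window follows the on-treatment calendar. Visits have a 3-day window either side, and no dated scans are set after early discontinuation, so its edges are approximate.
- The sizes are hypothetical, and the ORR shifts lie well inside intervals about 40 points wide. This stands, and it limits how serious the point is.

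**Conclusion.** Both parts hold on the visible text. Row 3 as written contradicts the PFS definition in SAP 5.1 and alone removes unscanned deaths between Study Day 43 and about Day 105. The ORR denominator drops early failures and can only push a non-zero ORR upwards. The two groups differ, and the PFS group is probably the smaller.

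Under the assumptions above (one to three unscanned patients per cohort, a 25% all-treated rate), ORR rises by 1 to 6 points. One or two Day 70 deaths raise 3-month PFS by 3.4 or 6.7 points and 6-month PFS by 1.8 or 3.3 points, with no change in the median. OS is unaffected. No primary objective is touched, but this should be corrected before analysis because the cohorts are small and the ORRs are compared externally. The denominators behind the external rates are not given.

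**What to change.** 1. For each expansion cohort, report ORR in the Safety Population, with patients who have no post-baseline scan counted as non-responders, beside the response-evaluable ORR. Use the all-treated figure in external comparisons and state its denominator.
2. Use either post-infusion or on-treatment throughout Protocol 7.11.1.2, Protocol 9.2.1 and SAP 4.1, and say whether an End of Treatment scan counts.
3. Reword row 3 of SAP Table 3 and Appendix 3 to: *no post-baseline tumor assessment and no death – censored at date of first dose*. An unscanned death is then an event unless the new-therapy row or the two-or-more-missed row applies.
4. In those two rows add: *or date of first dose if there is no post-baseline assessment*. Otherwise the last assessment is the screening scan, which precedes first dose.

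The cost is a few lines of wording in the SAP and protocol and one extra ORR column. No new data are needed. ORR, and possibly PFS, may look slightly less favourable. If the blacked-out text in SAP 6.6.1 already has an all-treated ORR, items 2 to 4 remain, with the denominator statement for external comparisons.
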